Hemoglobin	≥ 9 g/dL or ≥ 5.6 mmol/L without transfusion or erythropoietin dependency (≤ 7 days prior to registration)
Renal	
Serum creatinine OR Measured or calculated ^a creatinine clearance (GFR can also be used in place of creatinine or CrCl)	≤ 1.5 X upper limit of normal (ULN) OR ≥ 60 mL/min for subject with creatinine levels > 1.5 X institutional ULN
Hepatic	
Serum total bilirubin	≤ 1.5 X ULN OR Direct bilirubin \leq ULN for subjects with total bilirubin levels > 1.5 ULN
AST (SGOT) and ALT (SGPT)	≤ 2.5 X ULN OR ≤ 5 X ULN for subjects with liver metastases
Albumin	≥ 2.5 mg/dL
Coagulation	
International Normalized Ratio (INR) or Prothrombin Time (PT)	≤ 1.5 X ULN unless subject is receiving anticoagulant therapy as long as PT or PTT is within therapeutic range of intended use of anticoagulants
Activated Partial Thromboplastin Time (aPTT)	≤ 1.5 X ULN unless subject is receiving anticoagulant therapy as long as PT or PTT is within therapeutic range of intended use of anticoagulants
^a Creatinine clearance should be calculated per institutional standard.	

- 3.19a Adequately controlled blood pressure with or without antihypertensive medications defined as BP $< 150/90$ mmHg at screening.
- 3.19b Negative pregnancy test done ≤ 7 days prior to registration, for women of childbearing potential only.
- 3.19c Ability to complete Patient Medication and Blood Pressure diaries by themselves or with assistance.
- 3.19d Willing and able to provide informed written consent.

- 3.19e Willing to return to enrolling institution for follow-up (during the Active Monitoring Phase of the study).

*Note: During the **Active Monitoring** Phase of a study (i.e., active treatment and observation), participants must be willing to return to the consenting institution for follow-up.*

- 3.19f Willing to provide tissue and blood samples for correlative research purposes.(see Sections 6.12, 14.1 and 17.11).

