8.2 Dose Modifications for **Lenvatinib**-Related Toxicities

Treatment-Related Toxicity^{a, b} including hepatic injury and venous thromboembolic events	Management	Dose Modification
Grade 1 and Tolerable Grade 2		
	Continue Treatment	No change
Intolerable Grade 2^c or Grade 3^{d, e}		
First occurrence	Hold until resolved to Grade 0-1 or baseline ^f	14 mg orally once a day
Second occurrence (same toxicity or new toxicity)	Hold until resolved to Grade 0-1 or baseline ^f	10 mg orally once a day
Third occurrence (same toxicity or new toxicity)	Hold until resolved to Grade 0-1 or baseline ^f	4 mg orally once a day
Fourth occurrence (same toxicity or new toxicity)	Hold until resolved to Grade 0-1 or baseline ^f	Contact ACCRU Quality Assurance Specialist
Grade 4^g: Discontinue Study Treatment		

NOTE: See CTCAE v4 for grading:

Collect all CTC grades of AEs, decreasing and increasing grade.

- a. A delay of study treatment for more than 28 days (due to treatment-related toxicities) will require a discussion with the ACCRU Quality Assurance Specialist before treatment can be resumed (see protocol resource page).
- b. Initiate optimal medical management for nausea, vomiting, and/or diarrhea prior to any study treatment, interruption, or dose reduction.
- c. Grade 2 toxicities will be determined to be tolerable or intolerable by both the subject and investigator. If Grade 2 toxicity is determined to be intolerable, the dose of study drug will be reduced with or without dose interruption. Interruption for Grade 3 toxicities is mandatory.
- d. Weight loss of any grade may not require dose reduction, but should be managed based on the judgment of the investigator. Subjects with weight loss requiring dose interruption and reduction do not need to return to baseline weight to restart lenvatinib. Based on the judgment of the investigator, subjects may be restarted at a lower dose of lenvatinib for weight loss. Consultation with a registered dietician may be helpful in managing weight loss.
- e. Not applicable to abnormal clinical laboratory values that are not clinically relevant based on the judgment of the investigator (e.g., ALT, AST, γ -GTP values $< 10 \times$ ULN, and Na).
- f. For hematology toxicities, restart treatment after toxicity resolves to Grade ≤ 2 .
- g. Excluding laboratory abnormalities judged to be non-life-threatening, in which case manage as Grade 3.

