8.3 Dose Modifications for **Pembrolizumab**-Related Toxicities

CTCAE System/Organ/Class (SOC)	Adverse Event	Hold Treatment for Grade	Timing for Restarting Treatment	Treatment Discontinuation
Gastrointestinal Disorders	Diarrhea/Colitis	2-3	Toxicity resolves to Grade 0-1	Toxicity does not resolve within 12 weeks of last dose or inability to reduce corticosteroid to 10mg or less of prednisone or equivalent per day within 12 weeks.
		4	Permanently discontinue	Permanently discontinue
Endocrine Disorders	Other: Hypophysitis	2-4	Toxicity resolves to Grade 0-1. Therapy with pembrolizumab can be continued while endocrine replacement therapy is instituted.	Toxicity does not resolve within 12 weeks of last dose or inability to reduce corticosteroid to 10mg or less of prednisone or equivalent per day within 12 weeks.
Immune System Disorders	Infusion Reaction	3-4	Permanently discontinue	Permanently discontinue
Investigations	AST, ALT or Increased Bilirubin	2	Toxicity resolves to Grade 0-1	Toxicity does not resolve within 12 weeks of last dose.
		3-4	Permanently discontinue (see exception below) ^a	Permanently discontinue
Metabolism and Nutrition Disorders	Type 1 Diabetes Mellitus (if new onset) or Hyperglycemia	T1DM or 3-4	Hold pembrolizumab for new onset Type 1 diabetes mellitus or Grade 3-4 hyperglycemia associated with evidence of beta cell failure.	Resume pembrolizumab when subject is clinically and metabolically stable.
	Hypercalcemia	3-4	Toxicity resolves to Grade 0-1	Resume pembrolizumab when subject is clinically and metabolically stable.

CTCAE System/Organ/Class (SOC)	Adverse Event	Hold Treatment for Grade	Timing for Restarting Treatment	Treatment Discontinuation
Renal and urinary disorders	Renal Failure or Nephritis	2	Toxicity resolves to Grade 0-1	Toxicity does not resolve within 12 weeks of last dose or inability to reduce corticosteroid to 10mg or less of prednisone or equivalent per day within 12 weeks.
		3-4	Permanently discontinue	Permanently discontinue
Respiratory, thoracic and mediastinal disorders	Pneumonitis	2	Toxicity resolves to Grade 0-1	Toxicity does not resolve within 12 weeks of last dose or inability to reduce corticosteroid to 10mg or less of prednisone or equivalent per day within 12 weeks.
		3-4	Permanently discontinue	Permanently discontinue
Myocarditis	Grade 1 or 2	Withhold	Based on severity of AE administer corticosteroids	Ensure adequate evaluation to confirm etiology and/or exclude other causes

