	Grade 3 or 4	Permanently Discontinue		
	All Other Drug-Related Toxicity ^b	3 or Severe	Toxicity resolves to Grade 0-1	Toxicity does not resolve within 12 weeks of last dose or inability to reduce corticosteroid to 10mg or less of prednisone or equivalent per day within 12 weeks.
		4	Permanently discontinue	Permanently discontinue

NOTE: Permanently discontinue for any severe or Grade 3 drug-related AE that recurs or any life-threatening event.

- a. For subjects with liver metastasis who begin treatment with Grade 2 AST or ALT, if AST or ALT increases by greater than or equal to 50% relative to baseline and lasts for at least 1 week then subjects should be discontinued.
- b. Subjects with intolerable or persistent Grade 2 drug-related AE may hold study medication at physician discretion. Permanently discontinue study drug for persistent Grade 2 adverse reactions for which treatment with study drug has been held, that do not recover to Grade 0-1 within 12 weeks of the last dose.

8.4 Treatment Guidelines for Subjects Who Experience an Infusion Reaction Associated with the Administration of **Pembrolizumab**

Infusion Reaction Treatment Guidelines for Pembrolizumab		
CTCAE Grade	Treatment	Premedication at subsequent dosing
Grade 1 Mild reaction; infusion interruption not indicated; intervention not indicated	Increase monitoring of vital signs as medically indicated until the subject is deemed medically stable in the opinion of the investigator.	None

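### The pembrolizumab table in section 8.3 does not give one consistent rule for patients with liver metastases who enter with Grade 2 AST/ALT

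*Combined protocol and SAP*

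**What the plan says.** **Entry.** The laboratory limits in section 3.18 allow AST and ALT of "≤ 5 X ULN for subjects with liver metastases".

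**Grade 2 row.** The section 8.3 table has one liver row, "AST, ALT or Increased Bilirubin", split by grade. For Grade 2, pembrolizumab is held, the restart condition is "Toxicity resolves to Grade 0-1", and the discontinuation condition is "Toxicity does not resolve within 12 weeks of last dose". The row carries no footnote marker and no baseline alternative.

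**Grade 3-4 row.** The restart cell reads "Permanently discontinue (see exception below") and carries marker a. The discontinuation cell next to it calls for permanent discontinuation without any exception.

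**Footnote a.** It begins "For subjects with liver metastasis who begin treatment with Grade 2 AST or ALT" and requires discontinuation "if AST or ALT increases by greater than or equal to 50% relative to baseline", provided the rise lasts at least 1 week.

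**Use of baseline elsewhere.** For intolerable Grade 2 or Grade 3 events, the lenvatinib table in section 8.2 says "Hold until resolved to Grade 0-1 or baseline". Section 9.9a1 asks for closer monitoring of Grade 2 hepatic events until values are back at baseline.

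**The concern.** The protocol expects some patients to start at Grade 2, and footnote a measures their change from their own baseline. The Grade 2 row measures the same patients against Grade 0-1. The two parts of the table use different reference points for one group, and nothing says which governs.

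What is at stake is whether an eligible patient keeps or permanently loses a study drug, and whether two sites would handle the same laboratory values alike. After the same liver event, a return to the entry value can allow lenvatinib to restart while pembrolizumab may not.

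**Working it through.** The plan prints no figure to reproduce here. The check applies each rule literally to the same patient.

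**Step 1. Without any outside cut-off.** The entry value is Grade 2 (footnote a). The restart target is Grade 0-1 (Grade 2 row). Any Grade 0-1 value is lower than any Grade 2 value, so the target lies below the patient's own baseline. Suppose a drug-related rise within Grade 2 leads to a hold and the value then returns exactly to baseline. The event is still Grade 2, restart is not permitted, and at 12 weeks the discontinuation condition is met.

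**Step 2. Size of the gap.** The documents do not print the CTCAE grade limits. Assume that Grade 2 runs from above L = 3 to U = 5 x ULN. The 5 x ULN entry ceiling in section 3.18 fits that upper limit but does not prove it. As a range, L = 2.5 is also shown. For baseline b, the restart target lies 1 - L/b below baseline.

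| b (x ULN) | 1 - 3/b | 1 - 2.5/b |
|---|---|---|
| 3.2 | 6% | 22% |
| 4.0 | 25% | 38% |
| 5.0 | 40% | 50% |

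**Step 3. Where the row and the footnote collide.** A 50% rise is still Grade 2 when 1.5 x b is at most U, that is, b is at most 5/1.5 = 3.33 x ULN. This bound does not depend on L. Such baselines are themselves Grade 2 only if U exceeds 1.5 x L, which holds in both cases (5 against 4.5 for L = 3, and 5 against 3.75 for L = 2.5). Example: b = 3.2 gives 1.5 x 3.2 = 4.8 x ULN, still Grade 2. If the rise lasts at least 1 week, the row says hold and footnote a says discontinue.

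**Step 4. Where the Grade 3-4 row is unclear.** Grade 3 starts at a rise of U/b - 1. For b above 3.33 x ULN, some rises reach Grade 3 without reaching 50%:

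| b (x ULN) | Grade 3 begins at | Footnote a threshold, 1.5 x b |
|---|---|---|
| 3.5 | +43% | 5.25 |
| 4.0 | +25% | 6.00 |
| 4.5 | +11% | 6.75 |
| 5.0 | just above 0% | 7.50 |

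At b = 4, a 30% rise gives 5.2 x ULN. This is Grade 3 and below the 6.0 threshold. The restart cell points to an exception, the discontinuation cell does not, and footnote a says nothing about what happens below its threshold. A rise of 50% or more that lasts under 1 week is equally unaddressed.

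**The case against.** **Stronger readings that a reader might infer.** One is that a small rise costs the patient the drug while a larger rise is exempt from stopping, so that the table runs against severity. The text does not establish this. Footnote a states only when to discontinue, and the exemption is inferred from the word exception in the restart cell. The discontinuation cell is unqualified, Grade 3-4 is still listed among the grades for a hold, and the note under the table makes a recurring Grade 3 drug-related event a permanent stop. The under-50% window also disappears at baselines up to 3.33 x ULN on the assumed limits. What can be said is that the exemption is unclear.

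A second reading is that the ambiguity threatens the decision cut-offs of 2 and 4 successes among 25 patients per cohort. The documents do not give the share of patients with liver metastases and Grade 2 entry values, still less the share who would then be held and not recover. Patients who stop for toxicity go to Observation on the test schedule (section 13.3).

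**Limits on reach.** The table concerns pembrolizumab-related toxicity, so an unchanged Grade 2 baseline need not trigger a hold. Section 8.0 makes the modifications strict for two cycles only and guidelines afterwards. Two cycles are 2 x 21 = 42 days and 12 weeks are 84 days, so the 12-week stop may fall in the guideline period, unless a held cycle counts as still open (section 7.3 lets intervals lengthen). The lenvatinib table governs a different drug, so its baseline wording is a contrast and not a contradiction. The baseline wording in section 9.9a1 is for monitoring, not restart.

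**What stands.** These points narrow how often the problem arises. None of them says which line governs when it does, and guideline status leaves more room for sites to differ.

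**Conclusion.** The point holds as an inconsistency in the section 8.3 table for a group that sections 3.18 and 8.3 both anticipate. Three parts should be kept apart:

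- The Grade 2 row sets a restart target below the entry value and has no link to footnote a. This rests on the printed text alone and is the firmest part.
- The two cells of the Grade 3-4 row differ on whether footnote a is an exception, and no hold or restart rule is given for a rise under its threshold. The text alone shows this too; only the window sizes depend on the assumed limits.
- The Grade 2 row and footnote a require different actions at entry values up to about 3.33 x ULN. This needs the assumed Grade 2 limits.

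The number of patients affected cannot be derived from the documents, and no claim is made about power, alpha or the responder cut-offs. The correction is worth making because the rule can decide permanent loss of a study drug and its wording is strict in the first two cycles. Nothing here says which rule is clinically right.

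**What to change.** Reconcile the Grade 2 row, both cells of the Grade 3-4 row and footnote a for patients with liver metastases who enter at Grade 2, so that exactly one line governs each case:

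1. A drug-related rise that stays within Grade 2 and is under 50%.
2. A rise of at least 50%, lasting at least 1 week, that is still Grade 2.
3. A rise into Grade 3 of under 50%, or lasting under 1 week, including whether permanent discontinuation applies and, if not, which hold and restart rule does.
4. The restart target for a patient whose entry value is Grade 2, stated explicitly in relation to that value.

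The clinical content is for the sponsor and the drug supplier to set. The cost is one amended table row and footnote, with no extra tests and no change to the sample size or analysis.

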9.0 Additional Supportive Care

- 9.1 Antiemetics and intravenous fluids may be used at the discretion of the treating physician.
- 9.2 Blood products and growth factors should be utilized as clinically warranted and following institutional policies and recommendations. The use of growth factors should follow the published Recommendations for the Use of WBC Growth Factors: American Society of Clinical Oncology Clinical Practice Guideline Update. Journal of Clinical Oncology 2015;33:3199-3212.

- 9.3 Patients should receive full supportive care while on this study. This includes blood product support, antibiotic treatment, and treatment of other newly diagnosed or concurrent medical conditions. All blood products and concomitant medications such as antidiarrheals, analgesics, and/or antiemetics received from the first day of study treatment administration until 30 days after the final dose will be recorded in the medical records and on the case report form (CRF).
- 9.4 Diarrhea/Colitis:
- Subjects should be carefully monitored for signs and symptoms of enterocolitis (such as diarrhea, abdominal pain, blood or mucus in stool, with or without fever) and of bowel perforation (such as peritoneal signs and ileus).
- All subjects who experience diarrhea/colitis should be advised to drink liberal quantities of clear fluids. If sufficient oral fluid intake is not feasible, fluid and electrolytes should be substituted via IV infusion. For Grade 2 or higher diarrhea, consider GI consultation and endoscopy to confirm or rule out colitis.
- For **Grade 2 diarrhea/colitis** that persists greater than 3 days, administer oral corticosteroids.
- For **Grade 3 or 4 diarrhea/colitis** that persists >1 week, treat with intravenous steroids followed by high dose oral steroids. When symptoms improve to Grade 1 or less, steroid taper should be started and continued over no less than 4 weeks.
- 9.5 All treatments that the investigator considers necessary for a subject's welfare may be administered at the discretion of the investigator in keeping with the community standards of medical care. All concomitant medication will be recorded in the medical record and on the case report form (CRF) including all prescription, over-the-counter (OTC), herbal supplements, and IV medications and fluids. If changes occur during the trial period, documentation of drug dosage, frequency, route, and date may also be included on the CRF.
- 9.6 Apart from the assigned study drugs, subjects are **prohibited from receiving the following therapies** during the Screening and Treatment Phase (including retreatment for post-complete response relapse) of this trial:
- 9.61 Antineoplastic systemic chemotherapy or biological therapy
 - 9.62 Immunotherapy not specified in this protocol
 - 9.63 Chemotherapy not specified in this protocol
 - 9.64 Investigational agents other than pembrolizumab and lenvatinib
 - 9.65 Radiation therapy. NOTE: Radiation therapy to a symptomatic solitary lesion or to the brain may be allowed at the investigator's discretion.
 - 9.66 Live vaccines within 30 days prior to the first dose of trial treatment and while participating in the trial. Examples of live vaccines include, but are not limited to, the following: measles, mumps, rubella, varicella/zoster, yellow fever, rabies, BCG, and typhoid vaccine.

- 9.67 Systemic glucocorticoids for any purpose other than to modulate symptoms from an event of clinical interest of suspected immunologic etiology. The use of physiologic doses of corticosteroids may be approved after consultation with the ACCRU Quality Assurance Specialist (see protocol resource page).
- 9.68 Subjects who, in the assessment by the investigator, require the use of any of the aforementioned treatments for clinical management should be removed from the trial. Subjects may receive other medications that the investigator deems to be medically necessary.

The Exclusion Criteria describes other medications which are prohibited in this trial.

There are no prohibited therapies during the Post-Treatment Follow-up Phase.

9.7 Pneumonitis:

For **Grade 2 events**, treat with systemic corticosteroids. When symptoms improve to Grade 1 or less, steroid taper should be started and continued over no less than 4 weeks.

For **Grade 3-4 events**, immediately treat with intravenous steroids. Administer additional antiinflammatory measures, as needed. Add prophylactic antibiotics for opportunistic infections in the case of prolonged steroid administration.

9.8 Type 1 Diabetes Mellitus (if new onset, including diabetic ketoacidosis [DKA]) or Grade 3 Hyperglycemia, if associated with ketosis (ketonuria) or metabolic acidosis (DKA)

For **T1DM** or **Grade 3-4 Hyperglycemia**

- Insulin replacement therapy is recommended for Type I diabetes mellitus and for Grade 3-4 hyperglycemia associated with metabolic acidosis or ketonuria.
- Evaluate patients with serum glucose and a metabolic panel, urine ketones, glycosylated hemoglobin, and C-peptide.

9.9 Hypophysitis:

For **Grade 2 events**, treat with corticosteroids. When symptoms improve to Grade 1 or less, steroid taper should be started and continued over no less than 4 weeks. Replacement of appropriate hormones may be required as the steroid dose is tapered.

For **Grade 3-4 events**, treat with an initial dose of IV corticosteroids followed by oral corticosteroids. When symptoms improve to Grade 1 or less, steroid taper should be started and continued over no less than 4 weeks. Replacement of appropriate hormones may be required as the steroid dose is tapered.

9.9a Additional Supportive Care Guidelines for Pembrolizumab

Subjects should receive appropriate supportive care measures as deemed necessary by the treating investigator. Suggested supportive care measures for the management of adverse events with potential immunologic etiology are outlined below. Where appropriate, these guidelines include the use of oral or intravenous treatment with corticosteroids as well as

additional anti-inflammatory agents if symptoms do not improve with administration of corticosteroids.

Note that several courses of steroid tapering may be necessary as symptoms may worsen when the steroid dose is decreased. For each disorder, attempts should be made to rule out other causes such as metastatic disease or bacterial or viral infection, which might require additional supportive care. The treatment guidelines are intended to be applied when the investigator determines the events to be related to pembrolizumab.

It may be necessary to perform conditional procedures such as bronchoscopy, endoscopy, or skin photography as part of evaluation of the event.

9.9a1 Hepatic:

For **Grade 2** events, monitor liver function tests more frequently until returned to baseline values (consider weekly).

- Treat with IV or oral corticosteroids

For **Grade 3-4** events, treat with intravenous corticosteroids for 24 to 48 hours.

When symptoms improve to Grade 1 or less, a steroid taper should be started and continued over no less than 4 weeks.

9.9a2 Renal Failure or Nephritis:

For **Grade 2** events, treat with corticosteroids.

For **Grade 3-4** events, treat with systemic corticosteroids.

When symptoms improve to Grade 1 or less, steroid taper should be started and continued over no less than 4 weeks.

9.9a3 Management of Infusion Reactions: Signs and symptoms usually develop during or shortly after drug infusion and generally resolve completely within 24 hours of completion of infusion.

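### Section 9.4 sets the written steroid trigger for Grade 3-4 diarrhea/colitis 4 days later than for Grade 2 (day 8 against day 4), and no other section corrects it

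*Combined protocol and SAP*

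**What the plan says.** Section 9.4 gives two steroid instructions for diarrhea/colitis, separated by grade.

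- Grade 2: for an event "that persists greater than 3 days, administer oral corticosteroids".
- Grade 3 or 4: for an event "that persists >1 week, treat with intravenous steroids followed by high dose oral steroids". A taper of at least 4 weeks follows once symptoms fall to Grade 1 or less.

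Just before these lines, 9.4 says: "For Grade 2 or higher diarrhea, consider GI consultation and endoscopy to confirm or rule out colitis". The Grade 2 steroid line has no such extension to higher grades. Section 9.4 does not say how days are counted when Grade 2 worsens to Grade 3 or 4.

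Three other provisions in Section 9 bear on steroid use:

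- 9.5: treatment the investigator considers necessary "may be administered at the discretion of the investigator in keeping with the community standards of medical care".
- 9.67 prohibits "Systemic glucocorticoids for any purpose other than to modulate symptoms from an event of clinical interest of suspected immunologic etiology".
- 9.9a: "The treatment guidelines are intended to be applied when the investigator determines the events to be related to pembrolizumab". This paragraph comes after 9.4 and introduces measures set out below it.

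For study drug, 8.3 holds pembrolizumab for Grade 2-3 diarrhea/colitis and stops it permanently at Grade 4. Section 8.2 interrupts lenvatinib at Grade 3 and discontinues treatment at Grade 4, with optimal medical management of diarrhea to come first (footnote b).

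**The concern.** A steroid rule graded by severity would be expected to act at least as early in the sicker patient. This one acts later, and the Grade 3-4 line includes life-threatening Grade 4 events.

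The protocol's own drug information points the other way. Section 15.292 warns that diarrhea on pembrolizumab is occasionally severe enough to end in colonic perforation. Section 15.291 says that most of the drug's side effects can be reversed if corticosteroids are given promptly. The lenvatinib nursing guidance (15.192) sends staff back to the protocol's instructions for treating diarrhea, and notes that diarrhea may increase when immunotherapy is given at the same time. A site that follows 9.4 literally would hold off steroids in a Grade 3 patient at a point when it would already have treated a Grade 2 patient.

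This is a matter of patient safety and of consistent conduct across sites. It does not touch the primary endpoints, the sample size or the analysis.

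**Working it through.** The plan states no figure for this gap, so the check is a direct reading of the two triggers.

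**Inputs (Section 9.4)**

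| Grade | Must persist longer than | First met (onset = day 1) | Steroid |
|---|---|---|---|
| 2 | 3 days | day 4 | oral |
| 3 or 4 | 1 week = 7 days | day 8 | IV, then high-dose oral |

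**Gap.** 8 − 4 = 4 days; equally, 7 − 3 = 4 days. A continuous Grade 3-4 episode has no written steroid trigger on days 4, 5, 6 and 7, while a continuous Grade 2 episode has one from day 4.

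**Who falls in the gap.** A patient at Grade 2 for more than 3 days has met the oral-steroid trigger before any later worsening. The gap is therefore confined mainly to patients who start at Grade 3-4 or reach it within the first few days.

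**Does another section set an earlier trigger?**

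- 9.5 permits treatment at discretion but gives no timing.
- 9.67 permits steroids for suspected immune events but gives no timing.
- 8.2 and 8.3 say when to hold, reduce or stop study drug, not when to start steroids. After the first two cycles, 8.0 treats the modifications as guidelines.
- 9.9a concerns attribution and gives no timing.

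None sets an earlier Grade 3-4 trigger.

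**Comparison with the other immune events.** At Grade 3-4, pneumonitis (9.7) reads "immediately treat with intravenous steroids", and hypophysitis (9.9) reads "treat with an initial dose of IV corticosteroids followed by oral corticosteroids". Hepatic events (9.9a1) and nephritis (9.9a2) have no waiting period either. However, none of these four has a wait at Grade 2. They show that diarrhea/colitis is handled differently at both grades; they do not show that its Grade 3-4 wait in particular is a mistake. The finding rests on the order of the two triggers within 9.4.

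**With the Grade 3-4 trigger set no later than the Grade 2 trigger.** The latest start is day 4 in both grades, and the gap is 4 − 4 = 0 days.

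**The case against.** The strongest defense is that lenvatinib also causes diarrhea (59.4%, all grades, in the phase III trial described in Section 1.6), so a wait helps to sort out the cause. Lenvatinib continues at tolerable Grade 2, but interruption at Grade 3 is mandatory (8.2, footnote c). Its half-life is about 28 hours (15.15). Taking five half-lives as a conventional washout, 5 × 28 = 140 hours, and 140 / 24 is about 5.8 days. Grade 3 diarrhea that lasts more than a week off lenvatinib would then point away from lenvatinib. Tolerable Grade 2 diarrhea offers no such test.

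This is a possible reason, but the protocol does not state it, and footnote b may postpone the interruption on which it depends. It also fits poorly with 9.67, which confines systemic steroids to events of suspected immunologic cause. Once that suspicion exists, there is no reason for the sicker patient to wait longer. What stands is that the threshold may have been deliberate.

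It also stands that 9.4 forbids nothing. Earlier steroids are open to the investigator, study drug is held or stopped, and 9.4 asks for monitoring for perforation and consideration of endoscopy.

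A reader might go further in three ways that the documents do not support:

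- **That 9.4 gives Grade 2 patients steroids whatever the cause.** Section 9.4 states no attribution condition of its own, but 9.67 restricts steroids to suspected immune events, and 9.9a may reach 9.4 as well.
- **That the delay can reach 7 days.** A patient who worsens on day 4 and whose count restarts would meet the trigger on day 4 + 7 = 11, which is 11 − 4 = 7 days late. The text is silent on worsening and never states a restart. Only the 4 days can be read from it.
- **That diarrhea/colitis is shown to be an error by being the one event of five with a Grade 3-4 wait.** The other four have no wait at Grade 2 either.

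**Conclusion.** The written steroid trigger in 9.4 is inverted by severity, by 4 days. It conflicts with the protocol's own perforation warning and its emphasis on prompt steroids, and should be amended.

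The size rests on two readings: 1 week is 7 days, and persistence is counted in whole days from onset at a constant grade. The consequence for a patient depends on whether the site follows 9.4 literally or uses the discretion in 9.5.

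A reader might infer that the protocol compels delay, or that patients will be harmed. The first is wrong, because earlier steroids are permitted for suspected immune events. The second cannot be judged: the documents give no rate of Grade 3-4 diarrhea/colitis, so neither the number affected nor the harm can be estimated. Nor do they show whether the threshold is a slip or a choice.

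**What to change.** Amend 9.4 to state that:

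- for Grade 3-4 diarrhea/colitis of suspected immunologic cause, in line with 9.67, IV steroids followed by high-dose oral steroids start promptly, and in any case no later than the Grade 2 trigger;
- that limit is more than 3 days, counted from onset of Grade 2 or higher, and worsening does not restart the count;
- diarrhea judged due to lenvatinib or infection alone stays under 8.2 and medical management.

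The sponsor and the drug supplier should confirm the clinical wording and, if the longer wait was intended, record why.

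The cost is a short amendment with no new procedures, data or analyses. The clinical downside is that some Grade 3-4 episodes that would have resolved by day 7 will receive steroids, each with a taper of at least 4 weeks. Under 8.3, a patient who cannot get down to 10 mg of prednisone or equivalent per day within 12 weeks stops pembrolizumab. Episodes that last beyond day 7 would get the same regimen at least 4 days sooner. Limiting the change to suspected immune events keeps purely lenvatinib-related diarrhea out of the new exposure, as far as the investigator can tell the two apart.
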